## 6.6. Post-treatment Follow-up Period

At the end of the Treatment Period, Long-term Treatment Period, or Open-label Phase, as applicable, all subjects who discontinue treatment will be followed for an additional 156 weeks from last dose of IP received. Subjects will be monitored on week 9, followed by 24, 48, 72, 96, 120, 144 after the last dose up to week 156. End of study visit, will coincide with week 96, refer to Section 6.7. A visit window of  $\pm 7$  days is permitted.

The assessments and procedures that will be performed during this period are outlined in the Table of Events (see Table 3) and include but are not limited to:

Only for Follow-Up Week 9 post last dose, the below assessments will be performed:

- Iron chelating therapies: record on an ongoing basis up to week 9 Post-last dose (as detailed in Section 6.1).
- Other concomitant medications/therapies: such as surgery, radiation, systemic or any other therapy for the subject's disease - record on an ongoing basis up to week 9 Post-last dose..
- Concomitant procedures - record on an ongoing basis up to week 9 Post-last dose..
- Transfusion assessment - record on an ongoing basis up to week 9 Post-last dose (as detailed in Section 6.1). In addition, as detailed in Section 6.1, a subject diary will be available (refer to Section 6.1).
- Adverse event assessment regardless of causality- record on an ongoing basis up to Week 9 Post-last dose, and only related AE from Week 9 Post-last dose up to End of Study (refer to Section 6.1 for additional information).
- Malignancy and Pre-Malignancy Reporting - regardless of causality until End of Study. (refer to Section 6.1 and Section 10.5.2 for additional information)
- Vital signs (as detailed in Section 6.1)
- Weight
- Urine or serum medically supervised pregnancy test with a minimum sensitivity of 25 mIU/mL for FCBP
- For female subjects only - menstrual status
- Hematology (as detailed in Section 6.1)
- Serum chemistry (as detailed in Section 6.1)
- Urinalysis: microalbumin, creatinine, microalbumin/creatinine ratio (morning void; central lab)
- PK and ADA – refer to Sections 6.8 and 6.9
- Serum ferritin
- HRU

Post-treatment Follow-up monitoring at Week 24, 48, 72, 96, 120, 144 post last dose – assessments and procedures, that will be performed during this period are outlined in the Table of Events (see [Table 3](#)) and include but are not limited to:

- Adverse event assessment - record all AEs regardless of causality on an ongoing basis up to week 9 Post-last dose, and only related AE from week 9 Post-last dose up to End of Study (refer to [Section 6.1](#) for additional information).
- Malignancy and Pre-Malignancy Reporting - regardless of causality as SAEs until End of Study. Subjects are required to see the Investigator at least every 24 weeks to assess for malignancy and pre-malignancy, as per standard of care (refer to [Section 10.5.2](#) for additional information)

### 6.6.1. Early Discontinuation Follow-up Period

Subjects who discontinue before completing the double-blind treatment period (48 weeks) will continue to be monitored on week 9, followed by week 24, 48, 72, 120, 144 after the last dose.

The assessments and procedures that will be performed during this Early Discontinuation Follow-up Period are outlined in the Table of Events (see [Table 3](#)) and include but are not limited to:

- Iron chelating therapies: record on an ongoing basis (as detailed in [Section 6.1](#)) - this parameters is to be reported up to 48 weeks Post Dose 1 Day 1 or Week 9 post last dose whichever is the later date.
- Other post-treatment medications/therapies: such as surgery, radiation, systemic or any other therapy for the subject's disease - record on an ongoing basis - these parameters are to be reported up to 48 weeks Post Dose 1 Day 1 or Week 9 post last dose whichever is the later date.
- Post-treatment procedures - record on an ongoing basis - these parameters are to be reported up to 48 weeks Post Dose 1 Day 1 or Week 9 post last dose whichever is the later date.
- Transfusion assessment - record on an ongoing basis (as detailed in [Section 6.1](#)). In addition, as detailed in [Section 6.1](#), a subject diary will be available (refer to [Section 6.1](#)). - these parameters are to be reported up to 48 weeks Post Dose 1 Day 1 or Week 9 post last dose whichever is the later date.
- Adverse event assessment - record AEs regardless of causality on an ongoing basis until 9 weeks post last dose, related AE to be reported from week 9 Post-last dose until End of Study.
- Malignancy and Pre-Malignancy Reporting - regardless of causality as SAEs until End of Study. Subjects are required to see the Investigator at week 9 and at least every 24 weeks thereafter to assess for malignancy and pre-malignancy, as per standard of care (refer to [Section 10.5.2](#) for additional information)
- MRI for LIC (T2\* or R2, mg/g dw). The same MRI technique should be used within a subject throughout the study duration.

- MRI for abdominal ultrasound spleen measurement, unless splenectomized (as detailed in Section 6.1)
- MRI for myocardial iron (T2\*; ms).
- Bone mineral density of total hip and lumbar spine by DXA scan (as detailed in Section 6.1).
- HRU - this parameter is to be reported up to 48 weeks Post Dose 1 Day 1 or Week 9 post last dose whichever is the later date.
- Vital signs (as detailed in Section 6.1)
- Weight

### 6.7. End of Study Visit

Reasons for premature End of Study are provided in Section 11.2. The End of Study visit is the final scheduled visit for this study and can coincide with week 156 Post last dose.

The assessments and procedures that will be performed during the End of Study are outlined in the Table of Events (see Table 3) and include but are not limited to:

- Adverse event assessment - record AEs regardless of causality on an ongoing basis up to week 9 Post-last dose, and only related AE up to End of Study (refer to Section 6.1 for additional information).
- Malignancy and Pre-Malignancy Reporting - regardless of causality as SAE until End of Study (refer to Section 10.5.2 for additional information).

The reason for discontinuation should be recorded in the eCRF and in the source documents.

### 6.8. Pharmacokinetics

Serum samples will be collected to analyze luspatercept concentrations (PK) in all subjects as indicated in Table 3. Collection, processing, and shipping procedures for blood PK samples are provided in the study reference guide.

- Treatment Period: Doses 1 to 16: at predose (Dose 1 Day 1, must be collected before the first dose), Dose 2 Day 1, Dose 3 Day 1, Dose 4 Day 1, Dose 5 Day 1, Dose 6 Day 1, Dose 6 Day 8, Dose 6 Day 15, Dose 8 Day 1, Dose 10 Day 1, Dose 12 Day 1, Dose 14 Day 1, and Dose 16 Day 1
- Long-term Treatment Period: every 6 doses. ADA/PK sampling per Investigator's or Sponsor's discretion is allowed and should be recorded as an unscheduled visit

### 6.9. Anti-Drug Antibody

Serum samples will be collected for assessment of anti-drug antibodies (ADA) in all subjects. The maximum ADA monitoring period will be two years from dose 1 day 1 of double-blind Treatment Period. An additional blood draw is not needed for the anti-luspatercept antibody test.

The anti-luspatercept antibody test will be conducted for the following visits utilizing the PK samples obtained at the same visit:

- Treatment Period: Doses 1 to 16: Predose (Dose 1 Day 1, must be collected before the first dose), Dose 2 Day 1, Dose 4 Day 1, Dose 6 Day 1, Dose 8 Day 1, Dose 12 Day 1, Dose 16 Day 1.
- Long-term Treatment Period: every 6 doses.
- Open Label Phase: for placebo-cross-over subjects, only if positive at unblinding, continue every 6 doses up to 2 years from Dose 1 Day 1 of the double-blind Treatment Period. For subjects continuing treatment with luspatercept, only if positive at unblinding, every 6 doses up to 2 years from Dose 1 Day 1 of the double blinded treatment period..
- Post-treatment Follow-up (starting at Follow-up Week 9):
  - Before unblinding: every 24 weeks post last dose until the unblinding for up to two years from Dose 1 Day 1 of double-blind Treatment Period.
  - After unblinding, ADA monitoring every 24 weeks post last dose, only if subjects' last available ADA is positive and they have not reached the 2-year maximum limit for ADA monitoring.

ADA/PK sampling per Investigator's or Sponsor's discretion is allowed and should be recorded as an unscheduled visit.

CCI

### 6.11. Quality of Life

- TranQoL – Subjects will be asked to complete the quality of life questionnaire TranQoL at screening, and at Weeks 12, 24, 36 and 48 post Day 1 Dose 1, and every 12 weeks during the Long-term Treatment Period.
- SF-36 - Subjects will be asked to complete the quality of life questionnaire SF-36 at screening, and at Weeks 12, 24, 36 and 48 post Day 1 Dose 1, and every 12 weeks during the Long-term Treatment Period.

### 6.12. Screen Failures

For all subjects determined to be screen failures, the following information is to be captured in the subject's source documents and appropriate eCRF page(s): the date informed consent

document (ICD) was signed, demographics, the reason subject did not qualify for the study, and the Investigator's signature for the eCRF pages. The adverse events experienced by screen failure subjects will be collected from the date of signing consent to the day the subject is confirmed as screen failure. Relevant information will also be recorded on the Screening Log.

CELGENE PROPRIETARY INFORMATION

## 7. DESCRIPTION OF STUDY TREATMENTS

### 7.1. Description of Investigational Product(s)

Luspatercept will be provided by the Sponsor. Luspatercept for injection is formulated as a sterile, preservative-free, lyophilized cake/powder. Luspatercept for injection is available in 2 strengths, and when reconstituted, consists of 50 mg/mL luspatercept in a 10 mM citrate buffer-based solution (10 mM citrate, pH 6.5, 9% sucrose, 0.02% polysorbate 80). The drug product is packaged in a 3 mL glass vial in the following strengths:

- 25 mg/vial: The 25 mg/vial presentation contains 37.5 mg of Luspatercept protein. After reconstitution with 0.68 mL water for injection (WFI), each single-use vial will deliver at least 0.5 mL of 50 mg/mL luspatercept (25 mg)
- 75 mg/vial: The 75 mg/vial presentation contains 87.5 mg of Luspatercept protein. After reconstitution with 1.6 mL WFI, each single-use vial will deliver at least 1.5 mL of 50 mg/mL luspatercept (75 mg)

The recommended storage condition for luspatercept for injection (25 mg/vial and 75 mg/vial; lyophilized powder formulation) is 2-8°C. It is recommended that the reconstituted luspatercept for injection, at room temperature, be administered immediately. However, it may be held for up to 10 hours at 2°C to 8°C.

If not used immediately, the total in-use time of the reconstituted luspatercept for injection, from reconstitution to administration, must not exceed 10 hours.

Samples of luspatercept drug product, held at the recommended storage condition, have been shown to be stable through the labeled shelf-life.

Placebo to be used in the study will be sterile normal saline (0.9% sodium chloride for injection) administered as a SC injection. Sterile, normal saline will be prepared in syringes by the investigational site's designated individuals to match the active syringe. The doctor and subject will be blinded. The manufacturer's directions for placebo storage and handling are to be followed, as are standard clinical practices for ensuring sterility of the placebo.

### 7.2. Treatment Administration and Schedule

Luspatercept or placebo will be administered as a subcutaneous (SC) injection to subjects by the study staff at the clinical site and administration will be documented in the subject's source record. Subcutaneous injections will be given in the upper arm, thigh, and/or abdomen. Calculated doses requiring reconstituted volume greater than 1.2 mL should be divided into separate similar volume injections across two separate sites using the same anatomical location but on opposite sides of the body (example left thigh and right thigh). The maximum volume per SC injection should not exceed 1.2 mL. The maximum total dose per administration should not exceed 120 mg, which results in 2.4 mL maximum total volume after reconstitution. The injection sites can be rotated according to Investigator judgment, and the injections can be given in the following order as needed, for example: 1) right upper arm, 2) left upper arm, 3) right upper thigh, 4) left upper thigh.

Subjects will be assigned to treatment as per one of the following regimens:

- Luspatercept starting dose level 1 mg/kg SC once every 21 days
- Placebo SC once every 21 days

The investigational product should be administered according to the following criteria:

- **Pre-treatment/ pre-transfusion** Hb value is  $< 11.5$  g/dL and increase of Hb  $\leq 2.0$  g/dL compared to the pre-dose Hb of Day 1 of the previous treatment dose cycle, and
- Any related adverse events must be  $< \text{Grade } 2$  according to NCI CTCAE criteria ([Appendix C](#))
- WBC  $< 3 \times$  baseline. Corrected WBC values should be used to establish the baseline WBC. Baseline is equal to the highest WBC value between Screening WBC and Study Dose 1 Day 1.
- Leukopenia, neutropenia and/or thrombocytopenia should be  $< \text{Grade } 3$ , as per NCI CTCAE criteria ([Appendix C](#))
- $< 50 \%$  increase from baseline in transfusion burden in combination with shift from baseline (worsening) of  $< 2$  grades in leukopenia, neutropenia or thrombocytopenia

Please refer to [Table 5](#) for guidelines on dose modifications and dose delays.

Subjects must have Hb assessed and results available prior to each study drug administration. If a transfusion occurred prior to dosing, the pre-transfusion Hb should be considered for dosing purposes (ie, Hb  $\geq 14$  days post- transfusion).

Subjects must have blood pressure assessed prior to each study drug administration. Blood pressure values should be confirmed by means of two readings obtained approximately 10 minutes apart with the subject seated for approximately 10 minutes prior to initial reading.

Safety laboratory analyses and all assessments will be performed centrally (except otherwise stated in [Table 3](#)) during the double-blind Treatment Period. However, in addition to the blood draw or urine sampling for central analysis, blood draw or urine sampling for local laboratory assessments are only allowed in the following circumstances: cases when timely results are needed - eg, randomization, study treatment dosing decisions, hematology assessments between clinic visits, adverse event. Local laboratory data should be collected in the eCRF if relevant to dose administration, modification and AE, or when no central lab results were obtained.

Please refer to [Table 5](#) for guidelines on dose modifications and dose delays.

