## Overview of Key Efficacy Assessments

- The primary efficacy assessment will be:
  - Transfusion burden, calculated as units RBC per 12-week period, including the 12 weeks prior to Dose 1 Day 1, Week 13 to Week 24, and Week 37 to Week 48. Additional data obtained for each transfusion will include date, volume in mL, hematocrit of RBCs transfused, and pre-transfusion hemoglobin level.
- Other efficacy assessments will include:
  - Liver iron concentration (LIC, mg/g dw) measured by magnetic resonance imaging (MRI)
  - Daily dose of iron chelation therapy (ICT)
  - Serum ferritin
  - Total hip and lumbar spine bone mineral density (BMD) by dual energy x-ray absorptiometry (DXA)
  - Myocardial iron by MRI
  - Quality of Life using TranQoL, SF36
  - Healthcare resource utilization

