**Table 3: Table of Events (Continued)**

Assessments	Section	Screening/ Run-in Period Week -12 to Day -1	Treatment Period (double-blinded)				Long-term Treatment Period  (double- blinded) every 3-wk visits from Week 49 (ie, Dose 17 if no dose delays) /Day 1 (± 5 days)	Open-label Phase, every 3-wk visits from unblinding (± 5 days)		Day 22 Post Last Dose/ Treatment D/C 	Post-treatment Follow-up Period (± 7 days)			
			Luspatercept/ placebo Dose 1 Schedule (+7 days)	Luspatercept/placebo Doses 2 up to max 48 weeks Treatment (± 3 days)				Dose 1 for Placebo, Discont. 	Dose X Day 1 		Follow- up Week 9 (from last dose) 	Only if  Early Discont. – Follow-up Visits weeks 24, 48, 72, 96, 120, 144 (from last dose) 	All subjects: Follow- Up Visits weeks 24, 48, 72, 96, 120, 144 (from last dose) 	End of Study  / Follow- up week 156 (from last dose) 
				Day 1	Day 1	Day 8								
Hematology  (central lab; use local lab for predose hemoglobin, in case of AE, or between doses; reticulocytes and erythroblast to be measured by local lab; in Open-label Phase – use local labs)	6.1 to 6.6	X (within 4 wks prior Dose 1 Day 1)	X	X	X (Dose 6 only)	X (Dose 6 only)	X 	X	X	X	X	-	-	-
Serum Chemistry  (predose: central lab; use local lab in case of AE, or between doses; in Open-label Phase – use local labs)	6.1 to 6.6	X (within 4 wks prior Dose 1 Day 1)	X	X	-	-	X  (every 4 doses)	X	-	X	X	-	-	-
Urinalysis: microalbumin, creatinine, microalbumin/creatinine ratio (morning void; central lab; in Open-label Phase – use local labs)	6.1.1 to 6.6	X (within 4 wks prior Dose 1 Day 1)	-	X (every 4 doses)	-	-	X  (every 4 doses)	X	-	X	X	-	-	-

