 Vital signs (including heart rate, seated blood pressure [DBP and SBP], and temperature) will be measured at Screening, on Days 1 of each dose prior to administration of IP, at Treatment Discontinuation, at each visit during post-treatment Follow-Up, and at End of Study. Seated blood pressure should be confirmed by two separate measurements obtained predose and 10 minutes apart. The Investigator should report any clinically significant abnormal findings as adverse events.

 Pregnancy test is required for all female subjects of childbearing potential. Serum beta human chorionic gonadotropin (β-hCG pregnancy test (which must be negative) with a minimum sensitivity of 25 mIU/mL will be performed within 4 weeks prior Dose 1 Day 1. Urine (or serum) pregnancy test will be performed to assess subject eligibility within 72 hours prior to the first administration of IP, if the initial serum pregnancy test did not already occur with 72 hours of dosing (negative results required for IP administration). During the Treatment period urine or serum pregnancy test is allowed.

-  Hematology assessment includes RBC count, Hb, Hct, MCV, MCH, MCHC, RDW, WBC count with differential, absolute neutrophil count (ANC) and absolute lymphocytes, platelet and reticulocyte absolute values, and circulating erythroblast (nucleated RBC) counts. On dosing days, hemoglobin levels should be measured prior to dosing with IP to ensure Hb levels are within the acceptable ranges to allow luspatercept administration as per Section 7.2 and that luspatercept dose modification rules are followed as outlined in Table 5. Laboratory evaluations may be repeated more frequently if clinically indicated.
-  Serum chemistry (calcium, magnesium, phosphorus, blood urea nitrogen [BUN], creatinine, creatinine clearance, albumin, total protein, alkaline phosphatase, bilirubin [total, non-conjugated], AST/SGOT, ALT/SGPT, LDH and uric acid). If clinically significant, any or all laboratory evaluations should be reported as AEs and repeated more frequently, if clinically indicated.
-  For ADA test, additional blood draws are not needed. The test will be performed using the serum collected for PK samples. If ADA test is positive at the time of End of Study, the subject may need to return for additional ADA testing.
-  DXA scan of the lumbar spine and total hip for bone mineral density (BMD).

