#### 7.2.1.2. Dose Delay and Dose Reduction

Dose delay of luspatercept from the planned dosing schedule may occur due to increased hemoglobin or adverse events. Table 5 provides guidelines for dose modifications and dose delay.

Subjects can experience a dose reduction based on the change in mean Hb level (Hb not influenced by a transfusion) with respect to the last dose, as well as related adverse events, as detailed in Table 5. Hemoglobin not influenced by a transfusion should be considered for dosing, delays and discontinuation actions related to luspatercept. Hemoglobin not influenced by a transfusion is considered a Hb within 14 days post-transfusion. If a subject is experiencing a dose delay due to Hb increase, Hb measurement should occur every week.

If dose delay is 15 weeks or longer from the previous dose administered, including cases of elective surgery/hospitalization, the treatment should be discontinued. Dose delay for AE unrelated to the study drug, as per discretion of the Investigator are allowed. Assessments to be performed during the dose delay period are detailed in Section 6.

Celgene or its authorized representative should be notified of dose modification or interruption within 24 hours.

Dose reduction and dose delays guidelines are detailed in Table 5.

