**Table 5: Dose Delay, Dose Reduction and Discontinuation Guidelines:**

Event at the Day of Dosing	Action
Any related AE = Grade 2 a	Dose delay c until resolved to $\leq$ Grade 1 or baseline
Any related AE $\geq$ Grade 3 a	Dose delay c until resolved to $\leq$ Grade 1 or baseline, and then reduce dose by 25% d

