**Table 5: Dose Delay, Dose Reduction and Discontinuation Guidelines: (Continued)**

Event at the Day of Dosing	Action
> 2 dose reductions due to related AE a	Discontinue treatment
Increase in Hb >2.0 g/dL compared to pre-dose Hb of Day 1 of the previous treatment dose cycle b	Reduce dose by 25% d if ΔHb not influenced by RBC transfusions
Hb ≥ 11.5 g/dL b	Dose delay until Hb ≤ 11.0 g/dL
Worsening of Anemia	

A ≥ 50 % increase from baseline in transfusion burden in combination with an unexplained shift from baseline (worsening) of ≥ 2 gradesi in leukopenia, neutropenia or thrombocytopeniah.
	
Dose delayc and repeat WBC, neutrophils and platelets weekly for two consecutive weeks.
 
 
• If WBC, neutrophils and platelets are resolved to ≤ Grade 1 or baseline, continue with dosing at the same dose level.
 
• If WBC, neutrophils and platelets are Grade 2 and above baseline, then continue with dose delay until resolution to ≤ Grade 1 and evaluate for alternative explanations of cytopenia as per standard clinical practice.
 
• If shift (worsening) of ≥ 2 grades is maintained for ≥ 14 days or thrombocytopenia does not improve to < Grade 2 within 14 days and no alternative explanation is identified, then perform bone marrow assessment.                         
 
○ If hematologic malignancy is confirmed, discontinue treatmentg
 
○ If hematologic malignancy is not confirmed, then discuss future dosing with medical monitor.
 
 
 

WBC	

WBC counte ≥2X baseline in the absence of an associated condition (eg, infection or concomitant corticosteroid use)
	
Continue treatment, repeat WBC within 1 week
 
 
• If repeat WBC remains ≥ 2 X above baseline Investigator should assess the cause of increase to exclude hematologic malignancy as per standard clinical practice.
 
• If hematologic malignancy is confirmed, discontinue treatment.g
 

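### The last dosing criterion in Protocol Section 7.2 is stricter than the Table 5 anemia rule it should mirror, and the two conflict when dosing resumes

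*Protocol*

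**What the plan says.** **Protocol Section 7.2** lists conditions for giving a dose. The last one is a rise of less than 50%, worded as "increase from baseline in transfusion burden in combination with shift from baseline (worsening) of" fewer than 2 grades in leukopenia, neutropenia or thrombocytopenia.

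**Protocol Table 5 (Section 7.2.1.2), Worsening of Anemia**, delays the dose on a rise of at least 50%, worded as "increase from baseline in transfusion burden in combination with an unexplained shift from baseline (worsening) of" at least 2 grades in the same three counts. White cells, neutrophils and platelets are then repeated weekly for two weeks. If they have come back to at most "Grade 1 or baseline, continue with dosing at the same dose level". This resume step does not mention transfusion burden.

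**Links between the two.** Section 7.2 refers the reader to Table 5 for dose modifications and delays, and Section 7.2.1.2 says that the delay guidelines are set out there. Table 3, footnote 3, speaking of hemoglobin, cites both together: "to allow luspatercept administration as per Section 7.2 and that luspatercept dose modification rules are followed as outlined in Table 5". No sentence says which text prevails if they differ.

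**Consequence of a long hold.** Section 7.2.1.2: "If dose delay is 15 weeks or longer from the previous dose administered", treatment is to be discontinued. The same section asks for the sponsor to be told of any interruption within 24 hours.

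**The concern.** Section 7.2 is the go/no-go list at each dose, so its last bullet should be the negation of the Table 5 event. Negating a two-part condition means reversing both thresholds and also changing *and* to *or*. The bullet reverses the thresholds, keeps the joining phrase and drops the qualifier *unexplained*.

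Two sites could then treat the same subject differently. One follows Table 5 and resumes once counts recover. The other follows Section 7.2 and holds because transfusions are still raised. What is at stake is consistent dosing after a cytopenia and, if a hold runs on, an avoidable discontinuation.

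**Working it through.** No sample size, power or alpha figure is in dispute, so the check is logical.

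**Definitions.** A = transfusion burden at least 50% above baseline. B = a worsening of at least 2 grades in leukopenia, neutropenia or thrombocytopenia.

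- Table 5 event (delay): A and B, with B unexplained.
- Negation of that event: not-A **or** not-B.
- Section 7.2 as worded (dose allowed): not-A **and** not-B.

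| A | B | Table 5 event | Section 7.2, literal | Agree? |
|---|---|---|---|---|
| no | no | none | dose | yes |
| no | yes | none | bar | no |
| yes | no | none | bar | no |
| yes | yes | delay | bar | yes |

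Two of four cells agree. With the bullet written as the true negation, all four agree.

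**How far the two disagreeing cells go.** In both, Table 5 has no Worsening of Anemia event, so it is silent and not contrary. For B alone the gap is narrow. Cytopenia of Grade 3 or more has its own Table 5 row and its own Section 7.2 bullet, and the first Table 5 row, "Any related AE = Grade 2", already delays a related event. What remains is mainly a Grade 0 to 2 shift that is not judged related. Dropping *unexplained* adds one more difference: A with an explained shift is barred by Section 7.2 but is not a Table 5 event.

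**Restart, the direct contradiction.** Take baseline grades 0 to 2 and current grades 0 to 4, and keep the states that Table 5 calls recovered (Grade 1 or lower, or back to baseline). There are seven (baseline/current): 0/0, 0/1, 1/0, 1/1, 2/0, 2/1 and 2/2. In each, the shift is under 2 grades and the count is below Grade 3, so the count conditions of Section 7.2 are met. If A persists, Table 5 says continue and Section 7.2 says do not dose in all seven. If A has gone, there is no conflict in any.

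**Evidence on intent.** Three single-threshold bullets in Section 7.2 (related adverse events, white cells at 3 times baseline, Grade 3 cytopenia) are exact complements of Table 5 delay rows. The amendment justification also describes the anemia rule by reference to Table 5. Both suggest that the two texts were meant to match.

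**Why no length of hold is given.** Neither text states the window over which burden is measured. The Protocol Summary defines burden as "calculated as units RBC per 12-week period" for efficacy, Section 7.2.1.1 uses about 6 weeks for titration, and Section 3.1.1 uses a 24-week history for baseline. As an illustration, assume:

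- one extra 2-unit transfusion, u days before the withheld dose, on top of regular transfusion;
- a previous dose 21 days before the withheld one;
- counts recovered at day 14;
- a trailing window of W days.

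Burden falls back W − u days after the withheld dose, so the extra hold is max(0, W − 14 − u).

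- W = 84, u anywhere from 0 to 83: still barred at day 14 in 70/84 = 83% of timings; mean extra hold 2485/84 = 29.6 days.
- W = 42, u from 0 to 41: 28/42 = 67%; mean 406/42 = 9.7 days.
- A literal Section 7.2 would already have barred the previous dose had the rise been present then, so only about u = 0 to 20 is consistent with that reading. All timings are then barred at day 14, with mean (70 + 50)/2 = 60 days for W = 84 and (28 + 8)/2 = 18 days for W = 42.

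The latest release is day 21 + 84 = 105 (15 weeks) after the previous dose for W = 84, reached only at u = 0, and day 21 + 42 = 63 for W = 42. Two unstated choices move the mean from about 10 to 60 days and decide whether the 15-week stop can be reached at all. None of these figures is an estimate for this trial.

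**The case against.** The strongest reply is that a sensible site would not be misled. Section 7.2 sends the reader to Table 5 straight after the list, and resuming after a delay is a delay question on which Table 5 gives a specific instruction. The bullet can also be taken as shorthand for the Table 5 combination being absent. Much of this stands. A reader might infer that sites are left with no guidance on which text to follow, and that goes too far: the protocol repeatedly directs delay questions to Table 5. What it lacks is an explicit precedence rule, and the shorthand reading is not what the bullet says.

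A second reply is that the restart link is weak. Sections 6.2.1 and 6.3.1 mention the Section 7.2 criteria as the end point of repeat testing, and Section 6.4.1 does not cite Section 7.2 itself. That is fair, but Section 7.2 is not limited to any phase and its list governs each administration.

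A reader might also infer that the conflict touched the primary comparison. The documents do not support this. The anemia rule appears in the justification for the later amendment, inferred to be the one the SAP dates 11Dec2018, while the primary report used data up to 11MAY2018 (SAP Sections 2 and 5.1). Sponsor notification within 24 hours also gives a chance to query a hold, although no rule is given for settling it.

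**Conclusion.** Wrong as written, and minor. The last Section 7.2 criterion bars a dose on either condition, whereas Table 5 delays only on both. The two give opposite instructions in one situation: counts recovered after a Worsening of Anemia delay, with burden still at least 50% above baseline. This rests on reading the joining phrase in Section 7.2 as *and*, which is its plain meaning and the one Table 5 needs.

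It would be tempting to attach a typical extra hold or a number of lost subjects. The documents do not allow it: the burden window is unstated, and how often the two conditions occur together is not given. What can be said is that a hold lasting to 15 weeks from the previous dose ends treatment, and that a persistent rise in burden would produce such a hold under the literal rule. No completed analysis is affected.

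**What to change.** Replace the last Section 7.2 bullet with: *Do not dose if a ≥50% increase from baseline in transfusion burden occurs together with an unexplained worsening of ≥2 grades in leukopenia, neutropenia or thrombocytopenia; for resumption follow Table 5.* The resumption clause is needed. A subject who goes from baseline Grade 1 to Grade 3 and back to Grade 2 has a shift of only 1 grade, yet Table 5 keeps the delay until Grade 1.

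If the stricter rule is what the sponsor wants, change the Table 5 event and its resume step to match Section 7.2 instead.

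As a small related correction, both bullets of Section 6.4.1 cite Section 7.2.1.3 for criteria to resume. That is the Overdose section and contains none. Cite Section 7.2 in its place in both bullets.

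Cost: one bullet and two cross-references in a protocol amendment. Sample size, alpha and completed analyses are unchanged.
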